An Exploratory Prospective Trial of Rescue Acupuncture for the Treatment of
Acute Migraine.

NCT02764996

June 29, 2016

PROTOCOL FOR CLINICAL INVESTIGATION – NON-EXEMPT HUMAN
(Wilford Hall Ambulatory Surgical Center – WHASC)
PROTOCOL SUMMARY

1. Title:

An Exploratory Prospective Trial of Rescue Acupuncture for the Treatment of Acute Migraine.

FWH20150084H

2.0. Principal Investigator (PI):

WHASC PI:

Name	[name], D.O
Rank/Corps or Civilian Rating	Capt
Date of IRB Approved CITI Training & Date of Good Clinical Practice Training	07/09/15
Branch of Service	USAF
AD Mil/DoD Civilian/Ctr/Non-DoD Civ	AD MIL
Department & Base	Family Medicine Residency, Nellis AFB
Phone & [contact]
E-Mail Address & AKO/DKO E-Mail Address	[contact]

3.0. Research Plan:

3.1. Purpose:

To begin to determine if acupuncture is as effective as, or more effective than, rescue medication in the acute treatment of migraine.

3.2. Hypotheses, Research Questions or Objectives:

We will estimate the magnitude of effect that acupuncture has as an alternative to medication for treatment of acute migraine, as measured by change in headache pain severity 20-30 minutes, 2 hours, 4 hours 24 hours post treatment.

4. Brief Summary of the study:

This will be an exploratory observational trial of rescue acupuncture for the treatment of acute migraine in military beneficiaries to gain information to inform the power analysis of a larger, more definitive trial. We do not seek to definitively answer the question of whether this acupuncture protocol is effective; rather, we seek to estimate the proportion of migraine episodes that result in headache-free status 20-30 minutes, 2 hours, 4 hours, and 24 hours after an acupuncture treatment. Acupuncture treatments will be subject dependent, and points could include the N point (on scalp); various auricular points to include Shen Men, Point Zero, thalamus and Omega-2; body points to include Liver 2, Liver 3, Gall Bladder 20, bladder 10; and surface release over tense areas in the neck or shoulders. Researchers will document the points used, and data will be aggregated to determine overall effectiveness. Sub-group analysis by points will be performed to determine if there is more usefulness in 1 point or combination of points. These estimates will inform statistical power calculations for a future randomized controlled trial (RCT) that directly compares the effectiveness of Rescue Acupuncture with medical management of acute migraine with rescue medication. We will also assess the feasibility of this study protocol as well as patient receptivity and satisfaction.

5. Subjects:

Male and female DoD beneficiaries ages 18 years or older will be recruited at the Mike O’Callaghan Federal Medical Center (MOFMC). No special populations (e.g., pregnant women, children, military basic trainees, prisoners, detainees) will be recruited.

6. Inclusion/exclusion criteria:

Inclusion:

- Male and female DoD beneficiaries, age 18 years or older, who have been previously prescribed rescue medication to treat their acute migraine episodes.

Exclusion:

- Pregnant
- Absence of ear
- Active cellulitis of ear
- Ear anatomy precluding identification of acupuncture landmarks
- Use of Hearing Aids that preclude the insertion of needles

- Use of anticoagulants
- Unable to drive during rapid onset of migraine or inability to find someone to drive you

7. Number of Subjects: TOTAL NUMBER OF SUBJECTS (nation-wide/study-wide): 60

8. Use of an Investigational New Drug: N/A

9. Use of an Investigational Device: Seirin J-Type Acupuncture needles and Sedatelec ASP Original Gold Acupuncture needles, 510(k) exempt as Class II device under 21 CFR 880.5580

10. Use of a Placebo: N/A

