We will estimate the magnitude of effect that acupuncture has as an alternative to medication for treatment of acute migraine, as measured by change in headache pain severity 20-30 minutes, 2 hours, 4 hours, and 24 hours post treatment.

3.3. Significance:

Proof that acupuncture is superior to medication for treatment of migraine in military beneficiaries would result in less lost duty days, decreased medication use, and improved quality of life.

3.4. Military Relevance:

Migraine headaches are common in deployed US Army soldiers and exceed the expected prevalence. These headaches result in impaired duty performance and are a frequent cause of sick call visits. Migraine headaches tend to persist after deployment in many soldiers.⁶ A survey of a cohort of returning US Army Iraqi war veterans revealed that Soldiers with migraine made a total of 490 sick call visits for headache over a 3-month period of which 90 were for possible migraine. In all, 75% of the soldiers with migraine used over-the-counter analgesics and only 4% used triptans. Soldiers with migraine contacted 3 months after returning from Iraq had a mean of 5.3 headache days per month and 36% had a Migraine Disability Assessment Scale grade of 3 or 4.

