Various levels of acupuncture training have been taught to several hundred military physicians. A barrier to more widespread implementation has been lack of scientifically rigorous clinical trials to prove its worth in spite of the wide variety of anecdotal reports purporting its value in treating migraine. This trial will establish the efficacy acupuncture for acute migraine so that military beneficiaries can use less mind-altering medications. Additionally, many patients who have experienced traumatic brain injury develop chronic migraine that is refractory to medication, and acupuncture could be an important adjunct to this malady. Finally, management of medication side effects (i.e. chest pain in patients who take triptans) adds to costs that could be averted if acupuncture is effective. Proof that acupuncture is an effective treatment for acute migraine in military beneficiaries could result in fewer lost duty days, decreased medication use, and improved quality of life.

3.5. Background and Review of Literature:

Migraine is a recurring disorder characterized by attacks of severe headache generally associated with nausea, vomiting, and other neurologic symptoms. Duration is usually more than 4 hours and may last up to 72 hours with fluctuating intensity.¹ Migraine is commonly characterized as either episodic or chronic, depending on the frequency of attacks. Episodic migraine is more common, affecting up to 12% of the general population.² The direct medical costs of migraine headaches are approximately \$1 billion per year in the U.S.,³ with a national annual indirect burden of migraine estimated at \$12 billion (mostly attributed to absenteeism).³

Management of migraine focuses both on the treatment of acute attacks and the prevention of such attacks.^{4,5} The goals of migraine preventive therapy are to reduce attack frequency, severity, and duration; improve functional status/reduce disability; and improve response to acute treatments. The goal of acute treatment is typically to quickly eliminate or reduce the severity of migraine headache pain and associated symptoms. People who experience frequent migraine episodes often overuse

symptomatic medications. There are many “rescue medications” to choose from for the acute treatment of migraine, but side effects from pharmacologic approaches to migraine treatment can be considerable and often limit treatment options.

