4.9.4. Injury Compensation: N/A

4.9.5. Data Safety Monitoring:

The principal investigator will be responsible for the protocol safety monitoring. The PI will make study documents (e.g., consent forms, data pulls) and pertinent hospital or clinical records readily available for inspection by the local IRB and oversight staff for confirmation of the study data.

5.0. Alternatives:

Acupuncture for migraine is done in the Family Medicine Residency as part of standard of care. Subjects may choose to get this type of acupuncture without participating in this study.

6.0. Data Analysis:

6.1. Outcome Measures:

Primary outcome: Reduction of migraine headache pain from mild, moderate or severe to pain free, 20-30 minutes, 2 hours, 4 hours and 24 hours post treatment. Secondary outcomes: patient global assessment of preference for trying acupuncture vs rescue medications; overall satisfaction and perceived effectiveness of the treatment; reduction of symptoms other than migraine headache pain; and use of rescue medication within 12 hours of the initial treatment (irrespective of which study treatment received). These standardized outcome measures are commonly used in comparative effective trials of migraine rescue medications. Researchers will document the points used, and data will be aggregated to determine overall effectiveness. Sub-group analysis by points will be performed to determine if there is more usefulness in 1 point or combination of points.

6.2. Sample size estimation/power analysis:

We will treat 30 subjects. We will administer up to 6 acupuncture treatments for up to 6 different migraine episodes per subject over the course of 3 months. We will not formally test a hypothesis. Rather, we will determine the proportion of migraines that resolve (as assessed by headache severity) 20-30 minutes, 2 hours, 4 hours, and 24 hours after the start of an acupuncture treatment. These data will be used to inform power calculations for future studies.

6.3. Statistical Analysis:

We will use descriptive statistics to characterize the clinical response of subjects after acupuncture treatments.

6.4 Number of Subjects:

Number of subjects planned for MOFMC	Enrolled in Study	60	to result in	30	completing the study.
--------------------------------------	-------------------	----	--------------	----	-----------------------

TOTAL NUMBER OF SUBJECTS (nation-wide/study-wide): 60

7. **Duration of Study:** Approximate duration of the study: 2 years

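### The stated purpose and rationale claim efficacy and comparative effectiveness that this single-arm descriptive study, as its own summary recognises, cannot deliver

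*Combined protocol and SAP*

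**What the plan says.** The protocol speaks in two ways about what this study is for.

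**Efficacy or comparison**
- Section 3.1 (Purpose): "To begin to determine if acupuncture is as effective as, or more effective than, rescue medication in the acute treatment of migraine".
- Section 3.2 (Objectives, in both the summary and the body): "We will estimate the magnitude of effect that acupuncture has as an alternative to medication for treatment of acute migraine", measured by change in headache severity at each time point.
- Section 3.3 (Significance) argues from "Proof that acupuncture is superior to medication for treatment of migraine in military beneficiaries".
- Section 3.4 (Military Relevance): "This trial will establish the efficacy acupuncture for acute migraine".
- Section 3.5 (Background) presents a large phase III randomised comparison with rescue medication as what is being proposed.
- The Brief Summary, section 3.6.1 and section 6.1 each say that aggregated data will determine overall effectiveness.
- Section 6.1 defines a secondary outcome on rescue medication "irrespective of which study treatment received", as though there were more than one study treatment.

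**Estimation**
- The Brief Summary calls the study exploratory and observational and disclaims a definitive answer on effectiveness. It sets the aim as estimating how often treated episodes become headache-free, with feasibility alongside, and assigns the direct comparison to a future randomised trial.
- Section 6.2: "We will not formally test a hypothesis". It plans the proportion of migraines that resolve at each time point in 30 treated subjects, with up to 6 episodes each.
- Section 6.3 plans descriptive statistics only.

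**The concern.** A proportion of episodes that are pain-free after acupuncture combines natural resolution of the attack, the subject's expectation (which screening asks about) and any effect of treatment. At 2, 4 and 24 hours it may also include the effect of rescue medication, which section 3.6 allows once 20-30 minutes have passed without resolution. Read against sections 3.1, 3.2 and 3.4, such a proportion would be taken as an acupuncture effect, or as evidence on acupuncture against medication. Nothing in section 6.3 limits what may be concluded.

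The declared use of the results is also affected. The future trial compares acupuncture with medication, so its power calculation needs a response rate for each arm. This study supplies one of them, and the protocol does not say where the other will come from.

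**Working it through.** **1. The plan's own figure.** Section 6.4 gives 60 enrolled to yield 30 completing. No assumed rate, precision target, alpha, power or margin lies behind the 30, so it cannot be reproduced. The 60 agrees with 30 / (1 − 0.5) = 60, but the 50% loss is only inferred from those two numbers.

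**2. Is there a comparator anywhere?** Going through section 3.6:
- Screening records the names of rescue medications, not how past attacks responded to them.
- Each episode visit records medication use over the previous 7 days, again without a pain outcome.
- Follow-up records pain after acupuncture, and the type and amount of medication taken since.
- The 24-hour call asks which treatment the subject would prefer. That measures preference, not effectiveness.

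No subject contributes a pain outcome on medication alone or without treatment. Write pA for the pain-free proportion under the acupuncture strategy and pM for that under medication. The study observes pA only. The contrast pA − pM cannot be estimated, and more subjects would not change that.

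**3. What the design can give.** One proportion, with its interval:
- Each of 30 subjects counted once, exact (Clopper-Pearson) 95% interval: 6/30 = 20% gives 8% to 39%; 9/30 = 30% gives 15% to 49%; 15/30 = 50% gives 31% to 69%.
- All possible episodes, 30 × 6 = 180, allowing for clustering within subject: effective n = 180 / (1 + 5 × ICC), half-width = 1.96 × √(0.5 × 0.5 / effective n). With ICC = 0, effective n = 180 and the half-width is 7 points. With ICC = 1, effective n = 30 and it is 18 points. The documents give no ICC, so this is the full range.

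None of these intervals is for a difference from medication.

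**4. What the missing rate means for the future trial.** This is an illustration on assumed rates that are not in the documents: two-sided 5%, 80% power, pA = 0.40.

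n per arm = (z0.975 + z0.80)² × [pA(1 − pA) + pM(1 − pM)] / (pA − pM)², where the squared sum is 7.849 with unrounded z-values.

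| Assumed pM | Variance term / squared difference | n per arm |
|---|---|---|
| 0.20 | (0.24 + 0.16) / 0.04 = 10 | 79 |
| 0.25 | (0.24 + 0.1875) / 0.0225 = 19 | 150 |
| 0.30 | (0.24 + 0.21) / 0.01 = 45 | 354 |

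With z rounded to 1.96 and 0.84 the squared sum is 7.84, and the last two become 149 and 353. The spread is 354 / 79, about 4.5-fold, and comes wholly from a rate that this study does not measure.

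**The case against.** The strongest reply is that the Brief Summary already governs. It disclaims a definitive answer, names the proportion and feasibility as the aim, and defers the comparison. The title says exploratory, and sections 6.2 and 6.3 fit that reading. Section 3.1 is hedged as a beginning. Section 3.2 speaks of estimating and defines its measure as a change in severity, so its reference to medication could merely describe how acupuncture is used. The summary says that the estimates will inform the future power calculation, not that they suffice for it. Section 3.5 cites a randomised trial with a medication arm, so an outside source is at least in view.

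Much of this stands. Design, estimand and analysis agree with each other, and the conflict lies in the purpose, objective and rationale. It does not remove the point. Section 3.4 is unhedged and cannot be reconciled with the summary's disclaimer. The summary itself goes on to speak of determining overall effectiveness, and section 6.1 repeats this among the outcomes. The limit is absent from the objective and from the analysis section. The protocol does not say that the cited trial will supply the medication rate.

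A reader might also infer that the lack of a hypothesis test is a defect. It is not: an exploratory estimation study needs none, and only the missing comparator matters here.

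**Conclusion.** The protocol contradicts itself. The Brief Summary limits the study correctly, while sections 3.1 to 3.5 and the effectiveness wording in the Brief Summary, 3.6.1 and 6.1 claim efficacy or comparative effectiveness that a single-arm study cannot identify. This conclusion rests only on the absence of a comparator and on no assumed number. It is worth correcting because it governs what the trial may conclude, but it alters no planned procedure or calculation.

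Two stronger readings are not supported. A reader might infer that the study is invalid or must add a control arm; the estimation and feasibility aim in the Brief Summary is achievable with this design. A reader might also take the 79, 150 and 354 per arm as the size of an error in this plan. They rest on assumed rates, and any two-arm calculation varies with its second rate. They show only that the unmeasured medication rate drives the size of the future trial.

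**What to change.** - **3.1 and 3.2 (every occurrence):** state the aim as estimating the proportion of acupuncture-treated episodes that are pain-free, and describing the change in 0-3 pain severity, at each time point, together with feasibility. Keep the severity measure, since it is already an objective.
- **3.3 and 3.5:** mark the superiority claim and the phase III randomised trial as future work.
- **3.4:** delete the statement that this trial will establish efficacy.
- **6.1:** delete "irrespective of which study treatment received".
- **Brief Summary, 3.6.1 and 6.1:** replace the wording on determining overall effectiveness with describing overall response.
- **6.3:** add that the results are uncontrolled response proportions; that those at 2, 4 and 24 hours may include the effect of permitted rescue medication; that no conclusion on efficacy, or on effectiveness against medication, will be drawn; and that the medication-arm rate for the future power calculation will come from an external source.

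The cost is an amendment to the text and a more modest stated aim. Sample size, visits and data collection are unchanged.

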We will estimate the magnitude of effect that acupuncture has as an alternative to medication for treatment of acute migraine, as measured by change in headache pain severity 20-30 minutes, 2 hours, 4 hours, and 24 hours post treatment.

3.3. Significance:

Proof that acupuncture is superior to medication for treatment of migraine in military beneficiaries would result in less lost duty days, decreased medication use, and improved quality of life.

3.4. Military Relevance:

Migraine headaches are common in deployed US Army soldiers and exceed the expected prevalence. These headaches result in impaired duty performance and are a frequent cause of sick call visits. Migraine headaches tend to persist after deployment in many soldiers.⁶ A survey of a cohort of returning US Army Iraqi war veterans revealed that Soldiers with migraine made a total of 490 sick call visits for headache over a 3-month period of which 90 were for possible migraine. In all, 75% of the soldiers with migraine used over-the-counter analgesics and only 4% used triptans. Soldiers with migraine contacted 3 months after returning from Iraq had a mean of 5.3 headache days per month and 36% had a Migraine Disability Assessment Scale grade of 3 or 4.

Furthermore, a recent analysis examined the impact of migraine headaches on US Army Trainees. An anonymous, voluntary migraine questionnaire was administered to 1389 consecutive US Army Reserve Officer Training Corps cadets upon completion of 5 weeks of military training. Headaches were classified as definite migraine or possible migraine. Migraine frequency, prior diagnosis, number of missed or suboptimal training days attributable to migraine, patterns of analgesic use, and trainee characteristics associated with impaired training performance were identified. "... 54% of officer trainees completed the migraine questionnaire...The prevalence of definite migraine was 18% in all cadets...Migraines had been previously diagnosed in only 10% [of these]. During training, male trainees experienced a mean of 0.70 migraines/month compared with female trainees at 1.4 migraines/month. Only 3% of trainees meeting criteria for definite or possible migraine had ever been prescribed triptans. Eight percent of cadets experienced impaired training performance because of migraine resulting in 63 days of suboptimal or missed training. Characteristics associated with impaired training performance included a prior diagnosis of migraine, screening positive for definite migraine vs possible migraine, and a higher baseline frequency of migraine."⁷ The conclusions from the study revealed that migraine is common yet under diagnosed and undertreated in US Army officer trainees which adversely impacted military training. This data could be extrapolated to include all DoD since the trainee population is generally similar between the services. Migraines may be a characteristic that could place military trainees at risk for impaired training performance. Improved treatment of migraine would result in improved training performance which obviously directly impacts readiness.

Various levels of acupuncture training have been taught to several hundred military physicians. A barrier to more widespread implementation has been lack of scientifically rigorous clinical trials to prove its worth in spite of the wide variety of anecdotal reports purporting its value in treating migraine. This trial will establish the efficacy acupuncture for acute migraine so that military beneficiaries can use less mind-altering medications. Additionally, many patients who have experienced traumatic brain injury develop chronic migraine that is refractory to medication, and acupuncture could be an important adjunct to this malady. Finally, management of medication side effects (i.e. chest pain in patients who take triptans) adds to costs that could be averted if acupuncture is effective. Proof that acupuncture is an effective treatment for acute migraine in military beneficiaries could result in fewer lost duty days, decreased medication use, and improved quality of life.

3.5. Background and Review of Literature:

Migraine is a recurring disorder characterized by attacks of severe headache generally associated with nausea, vomiting, and other neurologic symptoms. Duration is usually more than 4 hours and may last up to 72 hours with fluctuating intensity.¹ Migraine is commonly characterized as either episodic or chronic, depending on the frequency of attacks. Episodic migraine is more common, affecting up to 12% of the general population.² The direct medical costs of migraine headaches are approximately \$1 billion per year in the U.S.,³ with a national annual indirect burden of migraine estimated at \$12 billion (mostly attributed to absenteeism).³

Management of migraine focuses both on the treatment of acute attacks and the prevention of such attacks.^{4,5} The goals of migraine preventive therapy are to reduce attack frequency, severity, and duration; improve functional status/reduce disability; and improve response to acute treatments. The goal of acute treatment is typically to quickly eliminate or reduce the severity of migraine headache pain and associated symptoms. People who experience frequent migraine episodes often overuse

symptomatic medications. There are many “rescue medications” to choose from for the acute treatment of migraine, but side effects from pharmacologic approaches to migraine treatment can be considerable and often limit treatment options.

Acupuncture is a nonpharmacologic treatment approach that has been proven to significantly reduce the frequency and severity of episodic migraines.^{6,7} However, there is (to our knowledge) only one published randomized controlled trial that evaluated the efficacy of acupuncture relative to a rescue medication for the acute treatment of migraine.⁸ This represents a significant research and knowledge gap. We propose to fill this gap by conducting a large, carefully designed, phase III, randomized controlled trial that directly compares the efficacy of acupuncture with rescue medications in the acute treatment of episodic migraine.

The needles being used are Seirin No. 3(0.20)x30mm stainless steel J-type with tube acupuncture needles which are approved by the FDA for use in acupuncture and will be used in accordance with their FDA approved labeling. As part of this study, the acupuncture needles themselves are not the object of the investigation, the process of acupuncture and the effect it has is what we are studying. The needles are merely the avenue we use to perform the acupuncture. According to 21 CFR 880.5580, an acupuncture needle is a device intended to pierce the skin in the practice of acupuncture.⁹ There are no known restrictions on the use of the acupuncture needles that prevent them from being used by qualified practitioners of acupuncture as they deem appropriate.

3.5.1. Bibliography:

1. Headache Classification Committee of the International Headache Society. The International Classification of Headache Disorders, 3rd edition (beta version). *Cephalalgia*. 2013; 33(9):629-80.
4. Silberstein SD. Practice parameter: evidence-based guidelines for migraine headache (an evidence-based review): report of the Quality Standards Subcommittee of the American Academy of Neurology.[Erratum appears in *Neurology* 2000 Jan 9;56(1):142]. *Neurology*. 2000;55(6):754-762.
